8. SAFETY REPORTING

Background regarding the safety reporting paragraph of this study.

According to the current Dutch SWAB guideline, combination therapy consisting of an azole and an echinocandin (e.g. anidulafungin, the IMP in this study) is one of the

treatment options for patients with IA. Another treatment option recommended in this guideline is azole monotherapy. In Belgium, azole monotherapy is the current standard of care. Combination therapy with voriconazole and anidulafungin has been studied in a preceding phase III study. In this study, the number of AE and SAE in the combination therapy arm was comparable to the azole monotherapy arm. Therefore, in this study 2 treatment options with a well-established safety profile will be compared.

Many if not the majority of the patients in this study will be receiving intensive chemotherapy or suffer from graft-versus-host-disease and its related AEs (e.g. anemia, leuco -or thrombocytopenia, diarrhea, mucositis, nausea, vomiting, alopecia, fever, bacteremia, fatigue, headache, bacterial and viral infections infection.

The study described in this protocol was designed as a pragmatic trial of which the goal is to compare two treatment options in a setting that simulates the treatment of IA in real-life as much as possible. This will the extrapolation of the study results as straightforward as possible.

For the reasons mentioned above, we think that registering all (S)AE will not only be very time consuming because the average number of AE per patient is expected to be very high but will not increase patient safety. We therefore will not register AE but only SAE with the limitations mentioned below.

8.1. Definitions

Serious adverse event (SAE)

A serious adverse event is defined as any untoward medical occurrence or effect that at any dose:

- " Results in death
- " Is a life-threatening event (i.e. the patient was at immediate risk of death at the time the reaction was observed)
- " Requires hospitalization or prolongation of an existing hospitalization
- Results in significant or persistent disability or incapacity
- " Is a congenital anomaly or birth defect
- Is an important medical event (i.e. important adverse events that are not immediately life threatening or do not result in death or hospitalization but may jeopardize the patient or may require intervention to prevent one of the above characteristics/consequences, including suspected transmission of infectious agents by a medicinal product).

Suspected unexpected serious adverse reaction (SUSAR)

A suspected unexpected serious adverse reaction is defined as all **suspected** Adverse Reactions (AR) which occur in the trial and that are both **unexpected** and **serious**.

Suspected adverse reactions are those AEs of which a reasonable causal relationship to any dose administered of the investigational medicinal product and the event is suspected. Unexpected adverse reactions are adverse reactions, of which the nature, or severity, is not consistent with the applicable product information (e.g. Investigator's Brochure for an unapproved IMP or Summary of Product Characteristics (SPC) for an authorized medicinal product).

Overdose

This refers to the administration of a quantity of a medicinal product given per administration or cumulatively, which is above the maximum recommended dose according to the authorised product information. Clinical judgement should always be applied.

Misuse

This refers to situations where the medicinal product is intentionally and inappropriately used not in accordance with the terms of the marketing authorisation.

Abuse

This corresponds to the persistent or sporadic, intentional excessive use of a medicinal product, which is accompanied by harmful physical or psychological effects.

Occupational exposure

This refers to the exposure to a medicinal product, as a result of one's professional or non-professional occupation. It does not include the exposure to one of the ingredients during the manufacturing process before the release as finished product.

Medication error

This is an unintended failure in the drug treatment process that leads to or has the potential to lead to harm to the patient.

In accordance to section 10, subsection 1, of the WMO, the investigator will inform the subjects and the reviewing accredited METC/IRB if anything occurs, on the basis of which it appears that the disadvantages of participation may be significantly greater than was foreseen in the research proposal. The study will be suspended pending further review by the accredited METC/IRB, except insofar as suspension would jeopardize the subjects' health. The investigator will take care that all subjects are kept informed.

8.2. Adverse event

8.2.1. Reporting of adverse events

Adverse events that do not fulfill the definition of Serious adverse Event will not be reported.

8.3. Serious Adverse Events

8.3.1. Reporting of serious adverse events

Serious Adverse Events (SAEs) will be reported from the first administration of treatment according to protocol until day 14 days after the last dose of the IMP or until the start of subsequent systemic therapy for the disease under study, if earlier.

Serious adverse events (including death) occurring after day 42 days should also be reported if considered at least possibly related to the investigational medicinal product by the investigator.

SAEs must be reported to HOVON Data Center within 3 days after the event was known to the investigator, using the SAE report form provided. This initial report should contain a minimum amount of information regarding the event, associated treatment and patient identification, as described in the detail in the instructions for the SAE report form. Complete detailed information should be provided in a follow-up report within a further 7 business days, if necessary.

The following events do not require to be reported as a serious adverse event:

- Relapse/Progression of the disease under study. However, death or complications as a result of disease progression should be reported as serious adverse events if occurring within 14 days after last dose of study drug.
- "Hospitalization for protocol therapy administration. Hospitalization or prolonged hospitalization for a complication of therapy administration will be reported as a serious adverse event.
- "Hospitalization for diagnostic investigations (e.g., scans, endoscopy, sampling for laboratory tests, bone marrow sampling) that are not related to an adverse event. Hospitalization or prolonged hospitalization for a complication of such procedures remains a reportable serious adverse event.
- " Prolonged hospitalization for technical, practical, or social reasons, in absence of an adverse event.
- Hospitalization for a procedure that was planned prior to study participation (i.e. prior to registration or randomization). This should be recorded in the source documents. Prolonged hospitalization for a complication of such procedures remains a reportable serious adverse event.

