5. TREATMENT OF SUBJECTS

5.1. Investigational product/treatment

Anidulafungin

Detailed information on anidulafungin, the investigational product used in this study can be found in the SPC. A short summary is given here. The information currently available on combination therapy with a triazole and an echinocandin for the treatment of IA is described below (6.2).

Mechanism of action

Anidulafungin is a semi-synthetic echinocandin, a lipopeptide synthesised from a fermentation product of Aspergillus nidulans. Anidulafungin selectively inhibits 1,3-8-D glucan synthase, an enzyme present in fungal, but not mammalian cells. This results in inhibition of the formation of 1,3-beta-D-glucan, an essential component of the fungal cell wall. Anidulafungin has shown fungicidal activity against Candida species and activity against regions of active cell growth of the hyphae of Aspergillus fumigatus.

Chemical Name

Anidulafungin has the chemical name 1-[(4R,5R)-4,5- Dihydroxy-N2- [[4"-(pentyloxy) [1,1':4',1"-terphenyl]- 4- yl]carbonyl]- Lornithine]echinocandin B.

Name of medicinal product

ECALTA 100 mg powder for concentrate for solution for infusion

Method of administration

For intravenous use only.

ECALTA should be reconstituted with water for injections to a concentration of 3.33 mg/mL and subsequently diluted to a concentration of 0.77 mg/mL.

Dosage & duration

Adult patients receive a loading dose on day-1 of 200mg IV, followed by 100 mg daily thereafter.

Anidulafungin will be given for at least 7 days but no longer than 28 days. Please note that this refers to the MITT primary endpoint population. In patients in which triazole resistance is demonstrated or in which the results of the resistance test are inconclusive, the treatment duration of combination therapy can be much longer. These patients are not included in the MITT primary endpoint population.

Intervention

Treatment with a triazole (voriconazole or isavuconazole or posaconazole) + anidulafungin IV. The triazole is administered for at least 6 weeks while anidulafungin is given for at least 7 and a maximum of 28 days.

Comparator

Treatment with a triazole (voriconazole or isavuconazole or posaconazole) for at least 6 weeks.

In both groups, the route of administration is according to the choice of the treating physician as well as the decision to perform or not perform therapeutic drug monitoring of the triazole drug.

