6.6. Dosages, dosage modifications and method of administration

Triazoles

All patients will receive triazole therapy as per standard of care and this will be initiated by the treating physician before the patient is included in the study. Therefore, the triazoles (voriconazole or isavuconazole or posaconazole) are not considered study drugs.

Voriconazole or isavuconazole or posaconazole will be dosed according to the SPC and according to the route of administration (IV or orally) that is preferred by the treating physician. However, the dose may be changed based on therapeutic drug monitoring levels according to the local standard of care.

Anidulafungin:

Anidulafungin (Ecalta) is available as an intravenous formulation only. It will be used at the licensed dose of a 200mg loading dose on day 1 and 100mg QD thereafter. No dose adjustment is needed in patients with renal or hepatic insufficiency of any grade.

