8.7. Follow-up of adverse events

All SAEs will be followed until they have abated, or until a stable situation has been reached. Depending on the event, follow up may require additional tests or medical procedures as indicated, and/or referral to the general physician or a medical specialist.

SAEs need to be reported from the first administration of treatment according to protocol until day 14 days after the last dose of the IMP or until the start of subsequent systemic therapy for the disease under study, if earlier.

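### SAE reporting ends 14 days after the last anidulafungin dose, so control patients have no defined end and early stoppers in the combination arm are uncovered up to day 42

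*Protocol*

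**What the plan says.** Section 8.3.1 sets the SAE reporting period as "from the first administration of treatment according to protocol until day 14 days after the last dose of the IMP". Reporting stops sooner if a new systemic treatment for the infection begins before then ("or until the start of subsequent systemic therapy for the disease under study, if earlier"). Section 8.7 repeats the rule ("SAEs need to be reported from the first administration of treatment according to protocol until day 14 days after the last dose of the IMP"). Neither section has a separate provision for the control arm.

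The next sentence of 8.3.1 adds: "Serious adverse events (including death) occurring after day 42 days should also be reported if considered at least possibly related" to the investigational product.

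The meaning of IMP is fixed elsewhere. Section 8 refers to "anidulafungin, the IMP in this study", and Section 6.6 says that "the triazoles (voriconazole or isavuconazole or posaconazole) are not considered study drugs". The comparator in Section 5.1 is "Treatment with a triazole (voriconazole or isavuconazole or posaconazole) for at least 6 weeks", with no anidulafungin. In the intervention arm, "anidulafungin is given for at least 7 and a maximum of 28 days". Section 5.1 limits that range to the MITT primary endpoint population and allows longer combination treatment when resistance is shown or the test is inconclusive. Under Section 3 the physician may stop the echinocandin from day 7 once there is a response and the patient can go home.

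Section 8.3.1 also exempts progression of the disease under study from SAE reporting, but makes death or complications from progression reportable within 14 days of the last dose of study drug.

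**The concern.** The end of SAE collection is tied to a drug that only one arm receives. For control patients the rule gives no date. For combination patients the date moves with a post-randomisation decision that depends on how well the patient is doing, so patients who respond early are observed for less time. The day-42 sentence reads as if everyone were under full reporting until day 42, which the preceding sentence does not provide.

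SAEs are the only adverse events collected: Section 8.2.1 excludes non-serious events and Section 7.3 plans no additional safety evaluations. Section 8.6 nevertheless requires an annual safety analysis that weighs efficacy against harm. Because this rule governs what sites send in, events that are never reported cannot be recovered at the analysis stage, whatever the SAP says.

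**Working it through.** **Inputs.** End of reporting = day of last IMP dose + 14 (8.3.1, 8.7). IMP = anidulafungin (8). Planned anidulafungin duration 7 to 28 days from day 1, MITT population (5.1). Day from which only possibly related SAEs are reported: after day 42 (8.3.1).

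**Reproducing the day-42 boundary.** A full planned course gives 28 + 14 = day 42. The boundary in 8.3.1 therefore matches the longest planned course, and only that one.

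**Combination arm, other stopping days.** Uncovered days = 42 − (last dose day + 14).

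| Last anidulafungin dose | Reporting closes | Share of 42 days | Days uncovered before the day-42 clause |
|---|---|---|---|
| Day 7 | 7 + 14 = day 21 | 21/42 = 50% | 42 − 21 = 21 (days 22 to 42) |
| Day 14 | 14 + 14 = day 28 | 28/42 = 67% | 42 − 28 = 14 (days 29 to 42) |
| Day 28 | 28 + 14 = day 42 | 42/42 = 100% | 0 |

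The middle row is not an extreme case: Section 6.2 reports a median of 14 days of combination treatment in the earlier randomised trial. Read literally, a possibly related SAE on day 30 in a patient who stopped on day 7 is not reportable, while one on day 50 is.

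**Size of the effect on counts.** If the SAE rate is assumed constant over time, the expected number of events is proportional to days observed. A patient followed for 21 days then contributes 21/42 = half the events of a patient followed for 42 days, with no difference in risk.

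**Control arm.** Reporting starts at first treatment according to protocol, and the comparator triazole is protocol treatment, so the start is defined. The end is last IMP dose + 14, and there is no IMP dose. The only other closing event is the start of subsequent systemic therapy, which never occurs in a control patient who stays on the assigned triazole. No end day can be computed. The progression exception has the same gap, because a control patient has no last dose of study drug.

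**Limits of the 21-to-42 range.** It is the planned MITT range. Stopping before day 7 or starting subsequent therapy closes reporting sooner. Treatment beyond day 28 outside the MITT population closes it later.

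**The case against.** The strongest reply is that this is a wording inconsistency with limited consequences. No endpoint in Section 7.1 is a safety endpoint, and Sections 9.1 and 9.2 describe no SAE analysis by arm. An SAP could restrict to a common period or use exposure-adjusted rates. Section 8.6 asks for a list and summary table of serious adverse reactions and a report on the medicine, and does not ask for arm-specific SAE rates. Survival status is recorded in both arms to day 168 (Appendix 2), and hospital and ICU days to week 24. Section 8 gives reasons for collecting little safety data, and Section 8.8 justifies the absence of a DSMB separately. Day 42 was probably meant as the common end.

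Much of this stands and limits the point, but it does not remove it. Exposure adjustment needs a defined observation period, which controls lack, and cannot restore events that sites were told not to report. If day 42 was intended for everyone, the text does not say so.

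Three stronger readings are tempting, and the documents do not support them:

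- **Reporting never opens for controls.** It opens at first protocol treatment; only the end is missing.
- **Controls are observed 1.3 to 2.7 times as long.** This takes the triazole as the IMP, giving at least 42 + 14 = 56 days, hence 56/42 = 1.3 and 56/21 = 2.7. Sections 6.6 and 8 exclude that reading. Since the triazole is given for at least six weeks, 56 would also be only a minimum.
- **SAEs cannot be compared between arms at all.** No such comparison is specified. What is compromised is any crude count or proportion by arm, not every possible safety summary.

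**Conclusion.** The point holds as a defect in the collection rule. As written, control patients have no defined end of SAE reporting. Combination patients on the planned MITT course have an end between day 21 and day 42 that depends on a response-linked decision. Up to 21 days (days 22 to 42) are uncovered for a patient stopping on day 7, even for possibly related events. Crude SAE counts by arm would then mix risk with observation time; the halving shown for a 21-day period assumes a constant event rate and is illustrative.

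The conclusion rests on reading IMP as anidulafungin alone, which Sections 6.6 and 8 support. The damage is confined to SAE data and the benefit-harm evaluation drawn from them. The primary endpoint, mortality follow-up, alpha and power are unaffected. The change should be made, but it does not threaten the trial's main conclusion.

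**What to change.** Reconcile Sections 8.3.1 and 8.7 around one calendar window:

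- Report all SAEs in both arms from randomisation to at least day 42, the boundary the text already implies, regardless of when anidulafungin stops or subsequent antifungal therapy starts.
- Where 14 days after the last anidulafungin dose falls later than day 42, continue to that date, so that patients treated beyond day 28 lose no coverage.
- Keep the clause on later SAEs considered at least possibly related to anidulafungin.
- Apply the same boundary to the disease-progression exception in 8.3.1.
- Summarise SAEs by randomised arm over the common window to day 42.

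The cost is a wording amendment and additional SAE forms, mainly for early stoppers and patients who change therapy. The extra forms may not be few, since Section 11.4 describes SAEs as very frequent in this population. For controls the added work depends on how long sites report now, which the protocol leaves open.

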8.3.2. Causality assessment of serious adverse events

The investigator will decide whether the serious adverse event is related to trial medication, i.e. any of the products from the protocol treatment schedule. The decision will be recorded on the serious adverse event report. The assessment of causality is made by the investigator using the following:

Causality term	Assessment criteria*
Certain	 Event or laboratory test abnormality, with plausible time relationship to drug intake Cannot be explained by disease or other drugs Response to withdrawal plausible (pharmacologically, pathologically) Event definitive pharmacologically or phenomenologically (i.e. an objective and specific medical disorder or a recognised pharmacological phenomenon) Rechallenge satisfactory, if necessary
Probable /Likely	 Event or laboratory test abnormality, with reasonable time relationship to drug intake Unlikely to be attributed to disease or other drugs Response to withdrawal clinically reasonable Rechallenge not required
Possible	 Event or laboratory test abnormality, with reasonable time relationship to drug intake Could also be explained by disease or other drugs Information on drug withdrawal may be lacking or unclear
Unlikely	 Event or laboratory test abnormality, with a time to drug intake that makes a relationship improbable (but not impossible) Disease or other drugs provide plausible explanations
Conditional / Unclassified	Event or laboratory test abnormalityMore data for proper assessment needed, orAdditional data under examination
Unassessable / Unclassifiable	 Report suggesting an adverse reaction Cannot be judged because information is insufficient or contradictory Data cannot be supplemented or verified

8.3.3. Follow up of serious adverse events

All serious adverse events will be followed clinically until they are resolved or until a stable situation has been reached. Depending on the event, follow up may require additional tests or medical procedures as indicated, and/or referral to the general physician or a medical specialist.

Follow up information on SAEs should be reported monthly until recovery or until a stable situation has been reached. The final outcome of the SAE should be reported on a final SAE report.

8.3.4. Processing of serious adverse event reports

HOVON Data Center will forward all SAE reports within 24 hours of receipt to the principal investigator.

The HDC safety desk will evaluate if the SAE qualifies as a suspected unexpected serious adverse reaction (SUSAR).

The SmPC will be used as a reference document for expectedness assessment.

Where reporting of SAEs to the ethics committee is required by national laws or regulations or by the procedures of the ethics committee, HOVON Data Center will report those SAEs by means of a six-monthly SAE line listing.

8.4. Reporting Suspected Unexpected Serious Adverse Reactions

The HDC Safety Desk, on behalf of the sponsor, will ensure the reporting of any SUSARs to the ethics committees (EC), the competent authorities (CA) and the investigators in compliance with applicable laws and regulations, and in accordance with any trial specific agreements between the sponsor and a co-sponsor.

Expedited reporting of SUSARs will occur no later than 15 days after HOVON Data Center had first knowledge of the serious adverse event. For fatal or life-threatening cases this will be no later than 7 days for a preliminary report, with another 8 days for a complete report.

The manner of SUSAR reporting will be in compliance with the procedures of the ethics committees and health authorities involved.

8.5. Reporting special situations

Overdose, abuse, misuse, medication error or occupational exposure are special reporting situations and must be reported to HOVON Data Center immediately.

Please inform HOVON Data Center of these events within 3 days hours after the event was known to the investigator by email ([contact]). Note that these special reporting situations in and of themselves are not AEs. If a special reporting situation results in an SAE, an SAE form should be completed and sent to HOVON Data Center (see section 12.3.1).

8.6. Annual safety report

The annual safety report will be combined with the annual progress report (see chapter 12.4).

In addition to the expedited reporting of SUSARs, the sponsor will submit, once a year throughout the clinical trial, a safety report to the accredited METC, competent authority, and competent authorities of the concerned Member States.

This safety report consists of:

 a list of all suspected (unexpected or expected) serious adverse reactions, along with an aggregated summary table of all reported serious adverse reactions, ordered by organ system, per study;

 a report concerning the safety of the subjects, consisting of a complete safety analysis and an evaluation of the balance between the efficacy and the harmfulness of the medicine under investigation.

